10.7. Appendix 7: Rash Management

Dengue symptomatic infection is known to result in skin rashes in a majority of patients.⁰ Rash may potentially also be related to the study drug and it may not be possible to differentiate between a rash secondary to DENV infection and one related to the study drug.

During the study, all rashes, where a causal relationship between the rash and the study drug cannot be excluded, will be discussed between the investigator and the Sponsor. **In case a causal relationship between the rash and the study drug cannot be excluded, then the following visits and assessments will be performed as indicated.** Unscheduled follow-up visits for close follow-up of rash will be performed based on the grade (severity) of the rash. At the investigator's discretion, additional visits and assessments can be performed.

The rash event should be captured in the Adverse Event Section of the CRF, and in more detail in the specific rash assessment pages of the CRF.

If a causal relationship between the rash and the study drug cannot be excluded, safety blood samples need to be taken during the (unscheduled) visits as described below. The following parameters need to be tested: AST, ALT, creatinine, erythrocyte sedimentation rate, and a complete blood cell count (including hemoglobin, hematocrit, red blood cell count, white blood cell count, neutrophils, lymphocytes, monocytes, eosinophils, basophils, and platelet count).

Participants should be informed that they should contact the investigator and visit the study site immediately (unscheduled visit, Day 0 of the rash) when they notice any rash. They should be advised to contact the investigator immediately if there is any worsening of the rash, if any systemic sign or symptoms appear, or if mucosal involvement develops.

Monitoring of the evolution of rash events will be performed as described in [Table 4](#) below. The following grades are based on the DAIDS Table for Grading the Severity of Adult and Pediatric Adverse Events, Corrected Version 2.1. (July 2017)^a with adaptations made by the sponsor.

^a DAIDS Table for Grading the Severity of Adult and Pediatric Adverse Events, corrected version 2.1, dated July 2017. Available at <https://rsc.niaid.nih.gov/sites/default/files/daidsgradingcorrectedv21.pdf> (accessed 20 April 2019)

Table 4: Management of Rash Events by Severity Grade

| | Definition | Study Drug Action | Activities by Day^a | Referral to Dermatologist and Dermatology Activities |
|---------------------------------|--|--|--|---|
| Grade 1 rash^b | Localized rash that is easily tolerated and/or may require one dose of medication. | Study drug intake may be continued at the investigator's discretion. | 
Day 0: required on-site unscheduled visit for initial rash evaluation, if participant is outside the study site.
 
 • Safety laboratory assessments are required. • Digital pictures^d should be taken (preferred within 24 hours) after the onset of the rash. • Cetirizine, levocetirizine, topical corticosteroids, or antipruritic agents may be prescribed. 
Day 1: safety blood samples and digital pictures^d should be taken.
 
After Day 7: If the rash is unresolved, additional unscheduled visits can be performed at the investigator's discretion. In case the rash evolves from a Grade 1 to a higher grade, additional unscheduled visits have to be conducted according to the guidelines for Grade 2 or Grade 3-4 rash, respectively.
 
Upon resolution/stabilization of the rash: digital pictures^d should be taken and the final rash assessment pages of the eCRF should be completed.
 | Not required |

| Grade 2 rash ^b | Definition | Study Drug Action | Activities by Day ^a | Referral to Dermatologist and Dermatology Activities |
|---------------------------|--|--|--|--|
| | 
Diffuse, maculopapular rash, or target lesions.
 
Symptomatic (pain/pruritus) but does not interfere with function and/or requires more than one dose of medication.
 | 
Study drug intake may be continued at the investigator's discretion
 | 
Day 0: required on-site unscheduled visit for initial rash evaluation, if participant is outside the study site.
 
 • Safety laboratory assessments are required. • Digital pictures^d of skin lesions should be taken (preferred within 24 hours) after the onset of the rash. • Cetirizine, levocetirizine, topical corticosteroids, or antipruritic agents may be prescribed. 
Day 1 and 7: safety blood samples and digital pictures^d should be taken.
 
After Day 7: If the rash is unresolved:
 
 • If there is an increase in AST/ALT of ≥ 2 times the ULN, participants should be followed weekly (or more frequently, at the investigator's discretion) with repeated local laboratory assessments and digital pictures^d until resolution of the AST/ALT abnormalities. • If there is no increase in AST/ALT, additional unscheduled visits (including local laboratory assessments and digital pictures^d) can be performed at the investigator's discretion. 
If the rash evolves from a Grade 2 to a Grade 3-4 rash, additional unscheduled visits have to be conducted according to the guidelines for Grade 3-4 rash
 
Upon resolution/stabilization of the rash: digital pictures^d should be taken and the final rash assessment pages of the eCRF should be completed
 | 
Not required
 |

| Definition | Study Drug Action | Activities by Day ^a | Referral to Dermatologist and Dermatology Activities |
|---|--|---|--|
| 
Grade 3 rash^b
 
Diffuse rash AND vesicles or limited number of bullae or superficial ulcerations of mucous membrane limited to 1 site,
 
OR elevations in AST/ALT >2x ULN,
 
OR body temperature $\geq 39.3^{\circ}\text{C}$ to $<40.0^{\circ}\text{C}$ ($\geq 102.7^{\circ}\text{F}$ to $<104.0^{\circ}\text{F}$),
 
OR eosinophils $>1000/\text{mm}^3$,
 
OR serum sickness-like reaction.
 | 
Must permanently discontinue and be withdrawn from the study; no rechallenge allowed.
 | 
Day 0: required on-site unscheduled visit for initial rash evaluation, if participant is outside the study site.
 
Day 0 and 1:
 
 • Safety laboratory assessments are required. • Digital pictures^d of skin lesions should be taken within 24 hours after the onset of the rash and on Day 1. 
Further visit(s): appropriate management and follow-up required until resolution of rash or until clinical stability is reached.
 
Days 2, 3, and 4: Only if the participant's AST/ALT on Day 0 and/or Day 1 of rash $>2x$ ULN and/or in case of rash progression:
 
 • Additional safety blood samples are required. • Digital pictures^d are to be taken. 
Day 5: Regardless of the Day 0/1 AST/ALT levels or rash progression:
 
 • Additional safety blood samples are required. • Digital pictures^d are to be taken. 
After Day 5: Weekly follow-up visits are required (or more frequently at the investigator's discretion) as long as Grade 3-4 rash is present. Once Grade 3-4 rash has resolved to \leqGrade 2 rash, follow-up should be done according to the instructions for follow-up visits for Grade 1 or Grade 2 rash, respectively.
 
 • Only if the participant's AST/ALT on Day 5 of rash is still $>2x$ ULN and/or in case of rash progression, additional safety blood samples and digital pictures^d are required at these weekly follow-up visits, until resolution or stabilization of the AST/ALT elevations. 
Upon resolution/stabilization of the rash: digital pictures^d should be taken and the final rash assessment pages of the eCRF should be completed.
 | 
Required^c
 
Biopsy required within 24hrs after onset of rash.
 |

| Definition | Study Drug Action | Activities by Day ^a | Referral to Dermatologist and Dermatology Activities | |
|---------------------------------|--|---|---|--|
| Grade 4 rash^b | Potentially life-threatening rash with: Extensive or generalized bullous lesions, OR ulceration of mucous membrane involving two or more distinct mucosal sites, OR Stevens-Johnson syndrome, OR toxic epidermal necrolysis. | Must permanently discontinue and be withdrawn from the study; no rechallenge allowed. | 
Day 0: required on-site unscheduled visit for initial rash evaluation, if participant is outside the study site.
 
Day 0 and 1:
 
 • Safety laboratory assessments are required. • Digital pictures^d of skin lesions should be taken within 24 hours after the onset of the rash and on Day 1. 
Further visit(s): appropriate management and follow-up required until resolution of rash or until clinical stability is reached.
 
Days 2, 3, and 4: Only if the participant’s AST/ALT on Day 0 and/or Day 1 of rash >2x ULN and/or in case of rash progression:
 
 • Additional safety blood samples are required. • Digital pictures^d are to be taken. 
Day 5: Regardless of the Day 0/1 AST/ALT levels or rash progression:
 
 • Additional safety blood samples are required. • Digital pictures^d are to be taken. 
After Day 5: Weekly follow-up visits are required (or more frequently at the investigator’s discretion) as long as Grade 3-4 rash is present. Once Grade 3-4 rash has resolved to ≤Grade 2 rash, follow-up should be done according to the instructions for follow-up visits for Grade 1 or Grade 2 rash, respectively.
 
 • Only if the participant’s AST/ALT on Day 5 of rash is still >2x ULN and/or in case of rash progression additional safety blood samples and digital pictures^d are required at these weekly follow-up visits, until resolution or stabilization of the AST/ALT elevations. 
Upon resolution/stabilization of the rash: digital pictures^d should be taken and the final rash assessment pages of the eCRF should be completed.
 | Required ^c Biopsy required within 24hrs after onset of rash. |

AE: adverse event; ALT: alanine aminotransferase; AST: aspartate aminotransferase

- a. Day 0 of the rash is the first day of investigator assessment and not the first day of rash as reported by the participant. The initial visit should be conducted as soon as possible after the participant contacts the investigator to report the AE (ie, preferably on Day 0). The initial visit and subsequent visits to manage the rash may require unscheduled visit(s).
- b. The participant should be advised to contact the investigator immediately if there is any worsening of the rash, if any systemic signs or symptoms appear, or if mucosal involvement develops. In case the rash evolves to a higher grade than that first observed, management of the rash should follow the guidelines indicated for the higher grade.
- c. If applicable, dermatologist visit should occur preferably within 24 hours after onset of rash.
- d. Digital pictures to be taken at the study site.

Notes:

Local laboratory assessments are to be used for rash management. A copy of the local laboratory reports should be de-identified and will be collected by the site manager.

A copy of the dermatologist's report, and biopsy if performed, should be made anonymous and will be collected by the site manager. Dermatologist fees for evaluating participants who experience a rash will be reimbursed by the sponsor.

Digital pictures will be de-identified and stored on the sponsor's secure server. Only the sponsor team members will have access to the sponsor's secure server.

Per investigator's discretion, the participant may be treated symptomatically until the rash resolves.

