8.3.2. Method of Detecting Adverse Events and Serious Adverse Events

Care will be taken not to introduce bias when detecting adverse events or serious adverse events. Open-ended and non-leading verbal questioning of the participant is the preferred method to inquire about adverse event occurrence.

Solicited Adverse Events

Signs and symptoms of DENV infection (DENV-infection associated AEs) will be collected by the investigator as solicited AEs. DENV infection signs and symptoms checklist may be compiled by any delegated study team member, and it may be used to assist in the collection of DENV infection associated AEs.

Solicited AEs are predefined events for which the participant is specifically questioned ([Table 2](#)). All AEs are evaluated using the gradings presented in [Table 3](#), the US FDA Toxicity Grading Table in Section [10.6](#), Appendix [6](#), or the rash management protocol in Section [10.7](#), Appendix [7](#).

Table 2: Solicited Adverse Events

| Systemic Reactogenicity | Laboratory Events |
|-----------------------------------|-------------------------------------|
| - Retro-orbital pain ^a | - Decreased Hemoglobin ^b |
| - Abdominal Pain ^a | - Neutropenia ^b |
| - Arthralgia ^a | - Elevated ALT ^b |
| - Fever ^b | - Thrombocytopenia ^b |
| - Headache ^b | - Leukocytosis ^b |
| - Nausea ^b | - Prolonged PT/INR ^b |
| - Fatigue ^b | - Prolonged PTT ^b |
| - Myalgia ^b | |
| - Loss of Appetite ^a | |
| - Vomiting ^b | |
| - Diarrhea ^b | |
| - Rash ^c | |

ALT = alanine aminotransferase; INR = international normalized ratio; PT = prothrombin time; PTT = partial thromboplastin time.

^a Grading according to [Table 3](#)

^b Grading according to the FDA Toxicity Grading Table in Section [10.5](#), Appendix [5](#).

^c Grading according to the rash management protocol in Section [10.7](#), Appendix [7](#).

Table 3: Grading of Solicited Adverse Events

| Local Reaction to Injectable Product | Mild (Grade 1) | Moderate (Grade 2) | Severe (Grade 3) | Potentially Life Threatening (Grade 4) |
|---|--|---|--|--|
| Retro-orbital pain, Arthralgia, Abdominal pain, | Event that is easily tolerated, may require 1 dose of medication/treatment | Event that interferes with daily activity or requires >1 dose of medication/treatment | Event that prevents daily activity | Life-threatening |

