10.6. Appendix 6: United States Food and Drug Administration Toxicity Grading Table

Source: the FDA Guidance document “Toxicity Grading Scale for Healthy Adult and Adolescent Volunteers Enrolled in Preventive Vaccine Clinical Trials” (September 2007)

A: Tables for Clinical Abnormalities

| Local Reaction to Injectable Product | Mild (Grade 1) | Moderate (Grade 2) | Severe (Grade 3) | Potentially Life Threatening (Grade 4) |
|--------------------------------------|---|--|--|--|
| Pain | Does not interfere with activity | Repeated use of non-narcotic pain reliever >24 hours or interferes with activity | Any use of narcotic pain reliever or prevents daily activity | Emergency room (ER) visit or hospitalization |
| Tenderness | Mild discomfort to touch | Discomfort with movement | Significant discomfort at rest | ER visit or hospitalization |
| Erythema/Redness* | 2.5 – 5 cm | 5.1 – 10 cm | >10 cm | Necrosis or exfoliative dermatitis |
| Induration/Swelling** | 2.5 – 5 cm and does not interfere with activity | 5.1 – 10 cm or interferes with activity | >10 cm or prevents daily activity | Necrosis |

* In addition to grading the measured local reaction at the greatest single diameter, the measurement should be recorded as a continuous variable.

** Induration/Swelling should be evaluated and graded using the functional scale as well as the actual measurement.

| Vital Signs * | Mild (Grade 1) | Moderate (Grade 2) | Severe (Grade 3) | Potentially Life Threatening (Grade 4) |
|---------------------------------------|------------------------------|------------------------------|------------------------------|--|
| Fever (°C) ** (°F)** | 38.0 - 38.4 100.4 - 101.1 | 38.5 - 38.9 101.2 - 102.0 | 39.0 - 40.0 102.1 - 104.0 | >40 >104.0 |
| Tachycardia - beats per minute | 101 – 115 | 116 – 130 | >130 | ER visit or hospitalization for arrhythmia |
| Bradycardia - beats per minute*** | 50 – 54 | 45 – 49 | <45 | ER visit or hospitalization for arrhythmia |
| Hypertension (systolic) - mm Hg | 141 – 150 | 151 – 155 | >155 | ER visit or hospitalization for malignant hypertension |
| Hypertension (diastolic) - mm Hg | 91 – 95 | 96 – 100 | >100 | ER visit or hospitalization for malignant hypertension |
| Hypotension (systolic) – mm Hg | 85 – 89 | 80 – 84 | <80 | ER visit or hospitalization for hypotensive shock |
| Respiratory Rate – breaths per minute | 17 – 20 | 21 – 25 | >25 | Intubation |

- * Participant should be at rest for all vital sign measurements.

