5.4.2.2. Vital Signs and Physical Examination Findings

The vital sign parameters that will be analyzed are temperature, pulse, systolic blood pressure, diastolic blood pressure, respiratory rate, oxygen saturation and I/O ratio.

Toxicity grades for the vital signs will be computed according to the United States Food and Drug Administration Toxicity Grading as presented in Table 9 (and appendix 6 of the protocol). No toxicity grades/abnormalities are defined for oxygen saturation and I/O ratio.

Vital signs will be plotted over time (days since first drug intake). All collected values will be displayed. In case of a toxicity/abnormality, the toxicity/abnormality will be flagged with the actual value on the plot.

- Different colors are used for toxicity grades 0-4.
- Different symbols are used for the direction of the toxicity grade (below/above).
- Normal ranges will be indicated for each vital sign.

Table 9: Vital Signs: Abnormality Criteria

Vital Signs	Mild (Grade 1)	Moderate (Grade 2)	Severe (Grade 3)	Potentially Life Threatening (Grade 4)
Fever (°C) **	38.0 - 38.4	38.5 - 38.9	39.0 - 40.0	>40
Fever (°F) **	100.4 - 101.1	101.2 - 102.0	102.1 - 104.0	>104.0
Pulse (bpm)				
Tachycardia	101-115	116-130	>130	
Bradycardia	50-54	45-49	<45	
Systolic blood pressure (mmHg)				
Hypertension (Systolic)	141-150	151-155	>155	
Hypotension (Systolic)	85-89	80-84	<80	
Diastolic blood pressure (mmHg)				
Hypertension (Diastolic)	91-95	96-100	>100	
Respiratory rate (breaths/minute)	17-20	21-25	>25	

Abnormal physical examination results will be listed in the patient profiles (date/time of examination, study day, body system, verbatim examination finding, clinically significant).

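### Table 4's Grade 3 rash fever item stops below 40.0 °C and Grade 4 has none, so for a possible drug rash with no other Grade 3 or 4 feature the mandatory stop lapses at the highest fevers

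*Protocol*

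**What the plan says.** Protocol Appendix 7 (Section 10.7) applies Table 4 when a causal link between a rash and study drug cannot be excluded. The relevant rows are:

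- **Grade 2.** The definition opens "Diffuse, maculopapular rash, or target lesions" and adds that the rash is symptomatic. It sets no temperature limit. The drug action is "Study drug intake may be continued at the investigator's discretion". Dermatologist referral is not required.
- **Grade 3.** A diffuse rash plus one of several features. One of them is "OR body temperature $\geq 39.3^{\circ}\text{C}$ to $<40.0^{\circ}\text{C", with the matching Fahrenheit band. The action is "Must permanently discontinue and be withdrawn from the study; no rechallenge allowed". Referral is required, as is a biopsy within 24 hours of onset.
- **Grade 4.** Extensive or generalized bullous lesions, or "ulceration of mucous membrane involving two or more distinct mucosal sites, OR Stevens-Johnson syndrome, OR toxic epidermal necrolysis". There is no temperature item. Drug action, referral and biopsy are as for Grade 3.

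Footnote b sends a rash that evolves to a higher grade to the management for that grade. Section 8.3.2, Table 2, footnote c also uses this appendix to grade rash as an adverse event: "Grading according to the rash management protocol in Section" 10.7.

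Fever itself is graded elsewhere. Appendix 6 gives Grade 3 as "39.0 - 40.0 102.1 - 104.0" (°C, then °F) and Grade 4 as anything above 40 °C. SAP Section 5.4.2.2 follows it: "Toxicity grades for the vital signs will be computed according to the United States Food and Drug Administration Toxicity Grading". Neither fever scale carries a drug action.

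**The concern.** Fever is one of the features that turns a diffuse rash from a matter of judgment into a mandatory stop. A rule of that kind should not relax as the sign worsens, yet this one requires a stop just below 40.0 °C and does not require it at or above 40.0 °C. Referral, biopsy and the Grade 3 follow-up schedule lapse with it.

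Rash is a named potential risk of the drug (Section 2.3.4), on the strength of two Grade 2 events in the first-in-human study that were judged very likely related. Those events came on Days 10 and 13 of longer dosing, and the half-life is 6.3 to 9.2 days (Section 2.2). A drug rash here could therefore appear after the last dose on Day 5. The drug stop would then be moot, but grade, referral and biopsy would still depend on this cell.

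**Working it through.** No sample size, power or error rate is involved. The check is whether the table, followed literally, gives an action that rises with temperature.

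**1. Is the cap a conversion or extraction slip?** Using °F = °C × 9/5 + 32:

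- 39.3 × 9/5 + 32 = 102.74, printed as 102.7
- 40.0 × 9/5 + 32 = 104.0, printed as 104.0

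Both bounds agree in both units, so the upper limit is in the text as written.

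**2. Apply the definitions.** Take a symptomatic diffuse maculopapular rash, causality not excluded, with no vesicles, bullae or mucosal ulceration, AST/ALT not above 2 × ULN, eosinophils not above 1000/mm³, no serum sickness-like reaction and no Grade 4 feature. Assign the highest grade met, with the stated temperature as the only reading while the rash is present.

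| Temperature | Rash grade (Table 4) | Fever grade (Appendix 6) | Drug | Referral and biopsy |
|---|---|---|---|---|
| 39.2 °C | 2 | 3 | may continue | not required |
| 39.3 to <40.0 °C | 3 | 3 | must stop | required |
| 40.0 °C | 2 | 3 | may continue | not required |
| 40.2 °C | 2 | 4 | may continue | not required |

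The Grade 3 cell mixes AND with OR. Reading it as diffuse rash plus any one item, or as diffuse rash with vesicles or else any one item, gives the same rash grades.

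**3. Does anything else restore the stop?**

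- Footnote b points to a higher grade, but no higher grade lists 40.0 °C or above.
- Appendix 6 and SAP Table 9 grade the fever but attach no drug action.
- Section 7.1 requires a stop if the investigator believes safety calls for it. It sets no temperature.
- Appendix 7 requires discussion with the sponsor, without a rule for the outcome.

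**4. How often could the Grade 3 band be missed?** Schedule of Activities footnote n sets two-hourly inpatient readings from 6 AM: 6, 8, 10, 12, 14, 16, 18, 20 and 22 h, which is 9 a day, or 10 if midnight is read. An ambulatory day has 1. Ambulatory visits are allowed on Days 3, 4, 5 and 6 and dosing is on Days 1 to 5 (Section 4.1). The overlap is Days 3, 4 and 5, so at most 3 of 5 dosing days rest on a single reading.

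**The case against.** The strongest reply is that clinical safeguards leave little room for harm.

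- Section 7.1 obliges the investigator to stop drug when he or she believes safety requires it, and the sponsor is consulted on every rash in scope. All doses are taken at the site (Section 6.1).
- With two-hourly inpatient readings, many participants above 40 °C will also have a reading in the Grade 3 band while the rash is present. The 3-of-5-days figure is an upper bound: ambulatory care is discretionary, and discharge needs satisfactory clinical status.
- Safety bloods are required on the first day of any rash in scope. Entry is allowed with AST or ALT up to 1000 U/L (Section 5.2), and raised ALT is a solicited dengue event, so some participants will already be Grade 3.
- Referral and biopsy that are not required are not forbidden.
- Widening the rule has a price. Appendix 7 says most patients with symptomatic dengue develop a rash and that it may be impossible to tell from a drug rash. More dengue rashes may be biopsied, and more participants withdrawn.

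All of this stands as a limit on reach. It does not repair the rule. The same safeguards exist at 39.5 °C, where the table still makes stopping mandatory, and the documents give no reason for relying on judgment alone at 40.2 °C. The price is also one the table already accepts from 39.3 °C.

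**Conclusion.** The defect is real and narrow, and it should be corrected. For a possible drug rash that is diffuse, maculopapular and symptomatic, with no other Grade 3 or 4 feature and no reading of 39.3 to <40.0 °C while it is present, a temperature of 40.0 °C or above leaves the rash at Grade 2. The mandatory stop, referral and biopsy then lapse. The rash would be recorded as Grade 2 beside a Grade 4 fever at 40.2 °C, against Grade 3 beside Grade 3 at 39.5 °C. The case most exposed is a first reading at or above 40.0 °C, especially on an ambulatory day. No frequency can be estimated from the documents.

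Three stronger inferences are not supported:

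- *That the plan has sites keep dosing any diffuse rash with fever of 40 °C or more.* Table 4 permits continuation and does not direct it. All the conditions above must hold, and Section 7.1 still applies.
- *That participants were affected.* The SAP reports that the trial ended for low enrollment after five participants. The documents do not show that any of them met these conditions.
- *That the results are distorted.* The SAP plans individual profiles with all vital signs plotted and flagged, so a Grade 2 rash beside a very high fever would be visible.

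**What to change.** In Table 4, change the Grade 3 fever item to *body temperature ≥39.3 °C (≥102.7 °F)*, deleting the upper bound in both units. Leave the rest of the table as it is. Footnote b needs no addition, because the table already routes an evolving rash to the higher grade.

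Adding a fever item of 40.0 °C or above to Grade 4 may look equivalent, but it is not. That cell is limited to potentially life-threatening rash and has no diffuse-rash condition. Read one way, a plain maculopapular rash at 40.2 °C would stay at Grade 2 and the gap would remain. Read the other way, any rash, even a localized one, would become Grade 4 through fever alone.

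The edit is to one cell, with no change to the planned sample size or analysis methods. The cost falls on a few more participants with a possible drug rash and very high fever. They would stop drug, be withdrawn, and have the Grade 3 bloods, visits, referral and biopsy, as the table already requires at 39.3 °C. Withdrawal could lose viral load data to Day 5 that the primary endpoint needs, against an assumed drop-out of about 4% (Section 9.2).

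This trial is closed. Appendix 8 gives alignment between studies as the reason for adding the updated rash section, so the sponsor should check whether other protocols carry the same cell.

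### The Grade 3 rash temperature criterion stops below 40.0 °C and Grade 4 has none, so in a narrow case a higher fever removes the mandatory stop, referral and biopsy

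*Protocol*

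**What the plan says.** Section 10.7 (Appendix 7) governs any rash for which drug causality cannot be ruled out: "In case a causal relationship between the rash and the study drug cannot be excluded, then the following visits and assessments will be performed". Table 4 then sets the actions by grade.

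- **Grade 2** covers a diffuse maculopapular rash or target lesions. On the drug, "Study drug intake may be continued" at the investigator's discretion. Dermatology referral is not required. Bloods and pictures are due on Days 0, 1 and 7.
- **Grade 3** is a diffuse rash with at least one further feature: vesicles, a few bullae or superficial mucosal ulceration at one site; AST/ALT above 2x ULN; eosinophils above 1000/mm³; a serum sickness-like reaction; or temperature in the band "OR body temperature $\geq 39.3^{\circ}\text{C}$ to $<40.0^{\circ}\text{C". The same band is printed in Fahrenheit, with an upper limit of <104.0 °F. The drug action is "Must permanently discontinue and be withdrawn from the study; no rechallenge allowed". Referral is required, and "Biopsy required within 24hrs after onset of rash". Weekly visits follow "as long as Grade 3-4 rash is present".
- **Grade 4** is "Extensive or generalized bullous lesions, OR ulceration of mucous membrane involving two or more distinct mucosal sites", Stevens-Johnson syndrome or toxic epidermal necrolysis. It carries the same stop, visits, referral and biopsy as Grade 3, and its definition does not mention temperature.

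None of the footnotes or notes to Table 4 says how to grade a rash with a temperature of 40.0 °C or more.

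**The concern.** A severity scale should not fall as the sign it measures worsens. Here it can: the mandatory action is heavier at 39.5 °C than at 40.5 °C for the same skin findings, and the protocol gives no reason for this. The population makes the criterion relevant. Every participant enters with reported fever, rash is common in symptomatic dengue, and Appendix 7 accepts that dengue rash and drug rash may be indistinguishable.

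What would chiefly be lost is the compulsory referral, the biopsy, the Grade 3 follow-up and the recorded rash grade. A site following the text exactly and a site following the likely intent would record different grades for the same rash. The lost stop matters less, because dosing lasts only five days and the drug has a long half-life.

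**Working it through.** **1. The cap is what the plan prints.** Using F = 1.8 × C + 32:
- 39.3 × 1.8 + 32 = 102.7 °F
- 40.0 × 1.8 + 32 = 104.0 °F

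Both match the Fahrenheit limits in Table 4, so the upper bound is not a text-extraction error.

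**2. Table 4 applied as a rule.** Take a drug-suspect diffuse rash with no vesicles, bullae or mucosal ulceration, AST/ALT not above 2x ULN, eosinophils not above 1000/mm³ and no serum sickness-like reaction.

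| Temperature readings during the rash | Grade as written | Upper bound deleted |
|---|---|---|
| All 39.2 °C or lower | 2 | 2 |
| Any from 39.3 to 39.9 °C | 3 | 3 |
| Qualifying readings only at 40.0 °C or above (40.0, 40.1, 40.5 and 41.0 tried) | 2 | 3 |

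The Grade 3 wording mixes AND with OR. The result is the same whether it is read as diffuse rash AND (any feature), or as (diffuse rash AND vesicles and so on) OR any other feature. If another feature is present, for example AST at 2.5x ULN, the rash is Grade 3 at every temperature and the gap does not arise.

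**3. Can readings miss the band?** Its width is 40.0 − 39.3 = 0.7 °C. A steady rise or fall is certain to give a reading inside the band only if its rate is at most 0.7 divided by the interval between readings. Footnote n to the Schedule of Activities sets the intervals: two-hourly for inpatients from 6 AM, none between midnight and 6 AM, and once daily for ambulatory visits.

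| Interval between readings | Fastest change always caught |
|---|---|
| 2 h (inpatient, daytime) | 0.7/2 = 0.35 °C/h |
| 6 h (overnight, if midnight is read) | 0.7/6 = 0.12 °C/h |
| 8 h (overnight, last reading 22:00) | 0.7/8 = 0.09 °C/h |
| 24 h (ambulatory) | 0.7/24 = 0.03 °C/h |

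Both the rise and the fall must be missed, unless only one of them happens during the rash.

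Two-hourly readings from 06:00 number 9 a day to 22:00, or 10 with midnight. Assuming at least one reading on Day 1, and for ambulatory participants at least one on Day 2, the totals over Days 1 to 5 are:
- Full inpatient: from 1 + 4 × 9 = 37 to 5 × 10 = 50.
- Ambulatory on Days 3 to 5: from 1 + 1 + 3 = 5 to 2 × 10 + 3 = 23.

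The maxima are upper limits, because Day 1 starts at first dose and ambulatory participants are discharged on Day 2. These figures show where the gap could open. They do not estimate how often it would.

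**4. Weight of the stop.** Protocol Section 2.2 gives a half-life of 6.3 to 9.2 days. Assuming simple exponential decline, the fraction of drug on board remaining 24 h after the last dose is 2^(−1/6.3) = 0.896 to 2^(−1/9.2) = 0.927, or about 90% to 93%. The two drug-related rashes described in Phase 1 began on dosing Days 10 and 13, under longer regimens whose timing may not carry over. A rash that late would come after this trial's five dosing days, when only referral, biopsy and follow-up are at stake.

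**The case against.** The gap in the text is hard to dispute, so the case against is about weight.

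**The case needs many conditions at once.** The rash must be drug-suspect and diffuse, with every other Grade 3 feature absent and no reading in the band. The laboratory criteria narrow it further: AST/ALT and eosinophils are drawn on rash Days 0 and 1 at Grade 2 as well, raised ALT is a solicited dengue event, and entry allows AST/ALT up to 1000 U/L. This stands, and it is why the number affected is probably small.

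**Safeguards remain.** Every such rash "will be discussed between the investigator and the Sponsor". Section 7.1 requires discontinuation if the investigator judges it best for the participant. Table 4, footnote b, tells participants to report systemic signs at once. Fever above 40 °C is graded separately as a Grade 4 adverse event under Appendix 6. These are real, but they rest on judgement or grade a different event. None of them makes referral or biopsy mandatory. Footnote b's rule to manage by the higher grade cannot help when no higher definition is met.

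**The biopsy may already be late.** It is timed from onset of rash, whereas Day 0 is the first investigator assessment, so at a single late visit the 24 h may have passed. This can reduce what is lost in that setting, but the referral requirement is still lost.

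**Fever is a weak drug-rash signal in dengue, and biopsy is a burden in a disease with a bleeding tendency.** Both are fair points, but they apply equally at 39.3 to 39.9 °C, where the plan already accepts the burden. They do not justify lighter action at a higher temperature. The two Phase 1 rashes were Grade 2 and no fever is described with either, so they do not show that febrile drug rash occurs.

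**The trial stopped with five participants.** SAP Section 1 records this, and it limits the practical effect here. It does not make the rule correct.

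**Conclusion.** The concern holds. As written, a drug-suspect diffuse rash whose only qualifying readings are at 40.0 °C or above, with no other Grade 3 or 4 feature, meets no grade above 2. It therefore loses the mandatory stop, referral, biopsy and Grade 3 follow-up that the same rash would receive at 39.3 to 39.9 °C. The conclusion follows from the printed definitions under either reading of the AND/OR wording.

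The size is limited. The gap is unlikely with two-hourly inpatient readings and more plausible with once-daily ambulatory readings, overnight, or at one unscheduled visit. The documents give no frequency of fever at 40.0 °C or more with rash, so no expected count can be given. Sample size, power, alpha and the primary analysis method are not affected. The threshold should be corrected because it is a stated safety rule that gives lighter mandatory action at a higher fever.

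**What to change.** In Table 4, delete the upper bound so that the Grade 3 criterion reads body temperature ≥39.3 °C (≥102.7 °F), and make the same change on the rash pages of the CRF. Adding ≥40.0 °C to Grade 4 would also close the gap, with the same actions. It is the weaker choice, because it would label a maculopapular rash in a dengue patient with high fever as potentially life-threatening.

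The wording costs one line. The few participants who move from Grade 2 to Grade 3 take on the existing Grade 3 actions: permanent discontinuation and withdrawal, referral, biopsy, Day 5 bloods and pictures, and weekly visits while the rash stays at Grade 3 or 4. A withdrawal before Day 5 could lose a little viral-load data for the primary AUC.

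The amendment history in Appendix 8 says the rash section was aligned with other studies. The sponsor should check whether the same bound appears in those protocols, which are not available here.
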